### 13.4.3 Adverse Events (AE)

AEs and the grade for each type of adverse event will be recorded for each patient separately for the first 12 cycles (mFOLFOX6 +/- atezolizumab) and the 6 months of

continuation of atezolizumab. Similarly, scores (0-4) and maximum score for each PRO-CTCAE item will be recorded for each patient separately for these two periods.

For CTCAE data, the frequency tables will be reviewed to determine the patterns. The overall adverse event rates will be compared between treatment groups using Chi-square test (or Fisher's exact test if the data in contingency table is sparse).

PRO-CTCAE data will, at minimum, be analyzed similarly to CTCAE data. Reasons for missed PRO-CTCAE assessments will be collected and we will describe the extent of missing data as well as its patterns and causes. The initial analysis of each PRO-CTCAE item will use all available scores in an analysis which mirrors the approach used for the CTCAE data. Supplemental analysis will use model-based multiple imputation incorporating baseline patient characteristics and physician-rated performance status (which is collected at each cycle). CTCAE data may be incorporated as axillary data into multiple imputation models for AEs which are captured by both PRO-CTCAE and CTCAE. Results from supplemental analysis will be descriptively compared to the results of the initial analysis to assess the robustness of results to missing data. Since a preferred or optimal statistical methodology for PRO-CTCAE data is yet to be determined, additional analyses of PRO-CTCAE data beyond those specified above may be undertaken based on the current state of the science at time of data maturity for this study.

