\*\*\* Patients will be followed for recurrence every 6 months (+/- 1 month) for the first two years after registration, and then once annually (+/- 1 month) for years 3-5 after registration. Recurrence follow-up will continue per the schedule above for 5 years after registration or until evidence of relapse, whichever comes first. See [Section 12.0](#) for survival follow-up.

- 1 For patients aged 12 to <18 years. Staging should be performed until the patient has reached Tanner Stage V.
- 2 Oxygen saturation should be assessed at rest and after 1 minute walk.
- 3 Solicited AEs are to be collected starting prior to treatment until off-treatment (see [Section 9.1](#)). Routine AEs are to be collected starting after registration until the end of survival follow-up. For patients who complete one cycle of FOLFOX prior to registration, the first routine AE assessment should take place after registration but prior to Day 1 Cycle 2 of FOLFOX; see [Section 9.3](#) for expedited SAE reporting.
- 4 Patients aged  $\geq 18$  years complete PRO-CTCAE by paper booklet ordered through the CTSU website. See [Section 9.1](#) for administration instructions. See [Appendix I](#) for PRO-CTCAE assessments for IRB submission and review only. See [Section 4.3](#) for ordering instructions. PRO-CTCAE booklets should be administered at the following time points:  $\leq 14$  days prior to registration; Day 1 of each Cycle, and at the end of treatment.
- 5 To be completed after registration but  $\leq 21$  days prior to treatment. See [Appendix I](#).
- 6 Albumin, alkaline phosphatase, total bilirubin, bicarbonate (or total CO2), BUN, calcium, chloride, serum creatinine, glucose, potassium, total protein, SGOT (AST), SGPT (ALT), and sodium.
- 7 Perform at baseline and then every 8 weeks (+/- 14 days).
- 8 For women of childbearing potential ([Section 3.2.6](#)). Must be done  $\leq 7$  days prior to registration.
- 9 Perform at baseline, 6 weeks (+/- 7 days) after end of FOLFOX, then every 6 months (+/- 1 month) for 3 years, then every 12 months (+/- 1 month) for an additional 2 years, or until relapse. After the end of FOLFOX treatment, the timing of CEA testing should correspond with timing of radiographic imaging studies, where possible, but more frequent testing is at provider discretion.
- 10 HIV-positive patients should complete a CD4 count and viral load  $\leq 28$  days prior to registration.

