## 7.0 TREATMENT PLAN/INTERVENTION

Protocol treatment is to begin within 14 days after registration.

**It is acceptable for individual therapy doses to be delivered  $\leq$  a 24-hour (business day) window before and after the protocol-defined date for a scheduled dose.** For example, if the treatment due date is a Friday, the window for treatment includes the preceding Thursday through the following Monday. In addition, patients are permitted to have a new cycle of immunotherapy/chemotherapy delayed up to 7 days for major life events (e.g. serious illness in a family member, major holiday, vacation that cannot be rescheduled) without this being considered a protocol violation. Documentation to justify this delay should be provided.

Patients with stage III, dMMR colon cancer will be randomized in 1:1 fashion to receive either Arm 1: mFOLFOX6 for 12 cycles total with atezolizumab starting at Cycle 1 or Cycle 2 of mFOLFOX6 with continuation of atezolizumab for a total of 12 months (6 months, i.e. 13 cycles of atezolizumab monotherapy), or Arm 2: mFOLFOX6 for 12 cycles, which is a total of 6 months. One cycle will be defined as 14 days of treatment.

Cycle 1 of mFOLFOX6 must be started within 10 weeks of surgical resection of the primary cancer. Please note that best practice is 3 to 6 weeks between surgery and Cycle 1 of chemotherapy. Cycle 1 of mFOLFOX6 may be given prior to registration. Once results of the local dMMR testing are complete and patients are found to have dMMR, patients may register and will then be randomized to Arm 1 or Arm 2. The standard of care for the time window between the start of mFOLFOX6 Cycle 1 and start of mFOLFOX6 Cycle 2 is 14 days, however, up to 28 days are allowed between Day 14 of Cycle 1 and Day 1 of Cycle 2 to allow for delays due to toxicity or patient decision making.

For patients who received one cycle of mFOLFOX6 prior to registration and who are on Arm 1, atezolizumab will start with Cycle 2 of mFOLFOX6. If Cycle 1 of mFOLFOX6 is administered prior to registration, it must be administered per [Appendix III](#). For patients who did not have a cycle of mFOLFOX6 prior to registration and who are on Arm 1, atezolizumab will start with Cycle 1 of mFOLFOX6.

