#### 9.1.1 Rave-CTEP-AERS integration

The Rave Cancer Therapy Evaluation Program Adverse Event Reporting System (CTEP-AERS) integration enables evaluation of post-baseline Adverse Events (AE) entered in Rave to determine whether they require expedited reporting and facilitates entry in CTEP-AERS for those AEs requiring expedited reporting.

All AEs that occur after start of treatment are collected in Medidata Rave using the Adverse Event form, which is available for entry at each treatment course or reporting period, and used to collect AEs that start during the period or persist from the previous reporting period. AEs that occur 30 days after the last administration of the investigational agent/intervention are collected using the Late Adverse Event form.

The CRA will enter AEs that occur prior to the start of treatment on a baseline form that is not included in the Rave-CTEP-AERS integration. AEs that occur prior to enrollment must begin and end on the baseline Adverse Events form and should not be included on the standard Adverse Events form that is available at treatment unless there has been an increase in grade.

Prior to sending AEs through the rules evaluation process, site staff should verify the following on the Adverse Event form in Rave:

- The reporting period (course/cycle) is correct; and
- AEs are recorded and complete (no missing fields) and the form is query free.

The CRA reports AEs in Rave at the time the Investigator learns of the event. If the CRA modifies an AE, it must be re-submitted for rules evaluation.

Upon completion of AE entry in Medidata Rave, the CRA submits the AE for rules evaluation by completing the Expedited Reporting Evaluation form. Both NCI and protocol-specific reporting rules evaluate the AEs submitted for expedited reporting. A report is initiated in CTEP-AERS using information entered in Medidata Rave for AEs that meet reporting requirements. The CRA completes the report by accessing CTEP-AERS via a direct link on the Medidata Rave Expedited Reporting Evaluation form. Contact the CTSU Help Desk at [name] or by email at [[contact]](mailto:[contact]) if you have any issues submitting an expedited report in CTEP-AERS.

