**9.1.2 Solicited Adverse Events**

The following adverse events are considered "expected" and their presence/absence should be solicited, and severity graded, at baseline and for each cycle of treatment by CTCAE, PRO-CTCAE, or both.

**NOTE:** PRO-CTCAE data should not be used for determining attribution, dose modifications, or reporting of serious adverse events.

CTCAE v5.0 Term	PRO-CTCAE v1.0 Term	CTCAE v5.0 System Organ Class (SOC)
The following adverse events should be solicited at baseline and for each treatment cycle:		
Hypothyroidism		Endocrine disorders
Abdominal Pain	Pain in the abdomen (belly area)	Gastrointestinal disorders
Constipation	Constipation	Gastrointestinal disorders
Nausea	Nausea	Gastrointestinal disorders
Fatigue	Fatigue, tiredness, or lack of energy	General disorders and administration site conditions
Anorexia	Decreased appetite	Metabolism and nutrition disorders
Cough	Cough	Respiratory, thoracic, and mediastinal disorders
Dyspnea	Shortness of breath	Respiratory, thoracic, and mediastinal disorders
Fever		General disorders
Blood bilirubin increased		Investigations
Neutrophil count decreased		Investigations
Platelet count decreased		Investigations
	Loose or watery stools (diarrhea)	Gastrointestinal disorders
	Vomiting	Gastrointestinal disorders
	Numbness or tingling in your hands or feet	Nervous system disorders

CTCAE v5.0 Term	PRO-CTCAE v1.0 Term	CTCAE v5.0 System Organ Class (SOC)
	Heartburn	Gastrointestinal disorders
Palmar-plantar erythrodysesthesia syndrome	Hand-foot syndrome (a rash of the hands or feet that can cause cracking, peeling, redness, or pain)	Skin and subcutaneous tissue disorders
	Rash	Skin and subcutaneous tissue disorders
	Itchy skin	Skin and subcutaneous tissue disorders
	Mouth or throat sores	Gastrointestinal disorders
The following adverse events should be solicited as clinically indicated*:		
Alanine aminotransferase increased 		Investigations
Aspartate aminotransferase increased 		Investigations
Hepatitis		Infections and infestations
Encephalitis infection		Infections and infestations
Kidney infection		Infections and infestations
Infective myositis		Infections and infestations
Infections and infestations – Other, specify 		Infections and infestations
Pneumonitis		Respiratory, thoracic, and mediastinal disorders
Colitis		Gastrointestinal disorders
Pancreatitis		Gastrointestinal disorders
Hyperglycemia		Metabolism and nutrition disorders

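### Section 13.4.3 gives the pre-registration PRO-CTCAE score no role; a prespecified baseline-adjusted comparison for the first 12 cycles would add a little precision at almost no cost

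*Combined protocol and SAP*

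**What the plan says.** Section 13.4.3 defines what is kept for each patient: "scores (0-4) and maximum score for each PRO-CTCAE item will be recorded for each patient separately for these two periods". The two periods are the first 12 cycles and the six months of atezolizumab continuation. For CTCAE data, "The overall adverse event rates will be compared between treatment groups using Chi-square test", with Fisher's exact test where cells are small. For PRO-CTCAE, "The initial analysis of each PRO-CTCAE item will use all available scores in an analysis which mirrors the approach used for the CTCAE data".

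Baseline information appears in 13.4.3 only in the handling of missing data: "Supplemental analysis will use model-based multiple imputation incorporating baseline patient characteristics and physician-rated performance status". The baseline item score is not named there. The section adds that the best method for PRO-CTCAE data is not yet settled and that further analyses may follow.

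The baseline score exists. Section 9.1.2 says that the listed events "should be solicited, and severity graded, at baseline and for each cycle of treatment by CTCAE, PRO-CTCAE, or both". Footnote 4 of the Study Calendar (Section 5.0) puts booklets at up to 14 "days prior to registration; Day 1 of each Cycle, and at the end of treatment". Section 4.3 makes the booklet a requirement of the main study, not of the optional quality-of-life substudy. Section 4.6 assigns arm after registration.

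**The concern.** The pre-registration score is measured with the same item, in nearly every adult, before arm is known. Such a score is usually among the better predictors of the later score. An unadjusted test leaves that information unused, so the arm difference is estimated with more variance than necessary. The clause on further analyses allows an adjustment but does not prespecify one, and there are 15 symptoms on which the choice could be made after seeing the data.

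Mirroring the CTCAE test also does not carry over the CTCAE collection rule. Section 9.1.1 states that "AEs that occur prior to enrollment must begin and end on the baseline Adverse Events form" unless the grade rises. No such rule is stated for the PRO booklets, so a raw per-arm PRO maximum can include symptoms that were already there. Recall is seven days, so the Day 1 booklet of the first on-study cycle describes almost only days before the first on-study dose, and 13.4.3 does not say whether it counts.

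At stake is the precision and clarity of a secondary safety description. The point is confined to the first 12 cycles. Section 7.0 gives "Arm 2: mFOLFOX6 for 12 cycles, which is a total of 6 months", so the second period has no on-treatment comparison.

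**Working it through.** **The plan's own figure.** Section 13.4.3 gives no power, alpha or standard deviation for PRO-CTCAE, so there is nothing to reproduce on this point. As a check of the arithmetic, Section 14.1.4 claims 91% power for the neuropathy scale with 490 patients. The standard error is 3.8 × √(2/245) = 0.343, and (1.9 − 0.76)/0.343 = 3.32. Power is Φ(3.32 − 1.96) = 0.913, which agrees.

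**Inputs.**
- From the documents: 350 adults per arm (13.2), 1:1 allocation, items scored 0 to 4, rash yes/no (Appendix I).
- Assumed: 340 per arm with data; cut at a maximum of 3 or higher; 30% of controls above it; an arm shift of 0.22 SD on a latent normal scale, giving 38%; latent baseline-to-maximum correlation r of 0.3 to 0.5; any baseline symptom in 65%, 40% or 5% of patients.

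**Unadjusted comparison.** Variance = 0.30 × 0.70/340 + 0.38 × 0.62/340 = 0.00131, so SE = 0.0362. Then 0.08/0.0362 = 2.21, and power = Φ(2.21 − 1.96) = 0.60. Simulation (4,000 replicates) gives 0.59 to 0.62.

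**Adjusted comparison.** Fit logistic regression on arm and baseline item score, then average the predicted risks over all patients under each arm. This targets the same marginal difference. With any baseline symptom in 40% or 65%:

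| r | variance ratio, adjusted/unadjusted | simulated power, unadjusted → adjusted |
|---|---|---|
| 0.3 | 0.947, 0.956 | 0.603 → 0.626; 0.593 → 0.623 |
| 0.5 | 0.869, 0.876 | 0.618 → 0.674; 0.606 → 0.666 |

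Putting the ratios into the closed form gives Φ(2.21/√0.95 − 1.96) = 0.62 and Φ(2.21/√0.87 − 1.96) = 0.66, in line with the simulation. The mean risk difference is 0.080 to 0.082 unadjusted and 0.079 to 0.081 adjusted. Type I error of the adjusted test is 0.045 and 0.049.

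**Less favourable items.**
- Any baseline symptom in 5%, control rate 30%: 0.601 → 0.609 (r = 0.3) and 0.587 → 0.609 (r = 0.5).
- Control rate 10%, any baseline symptom in 40%: 0.416 → 0.435 and 0.423 → 0.451.
- Control rate 5%, any baseline symptom in 40%: 0.310 → 0.316 and 0.310 → 0.330.
- Control rate 5%, any baseline symptom in 5%: 0.278 → 0.285 (variance ratio 1.005, so no visible gain) and 0.314 → 0.326.
- Yes/no item, 30% in controls, present at baseline in 5 to 15%: gains of 1 point at r = 0.3 and 3 to 4 points at r = 0.5.

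Across items with rarer severe scores or few baseline symptoms, the variance falls by about 1 to 9%.

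**Cost if baseline is uninformative.** For a mean score the variance ratio is (1 − r²)(1 + 1/(N − 4)). At r = 0 and N = 700 it is 1.001, a loss of about 0.1%.

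**Scale matters.** The log odds ratio (SE) is 0.36 (0.163) unadjusted, and 0.38 (0.167 to 0.168) and 0.42 (0.175 to 0.177) adjusted at r = 0.3 and 0.5. The conditional odds ratio is not more precise, so the gain has to be reported on the risk-difference scale.

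**Sparse items.** With 2% at score 3 or higher and baseline symptoms in 5%, the logistic fit diverged in about 9% of null replicates at r = 0.3 and 2% at r = 0.5.

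**The case against.** The strongest reply is that nothing here is wrong. The objective is to describe the safety profile; no power target is set for PRO-CTCAE, and the items are tested one by one without multiplicity control. Section 13.4.3 calls the unadjusted comparison an initial analysis and a minimum, and says openly that the method is still developing. Where a PRO comparison is meant to be inferential, in 14.1.4, the plan does use change from baseline. All of this stands, and it limits the point to an improvement. It does not remove it: 13.4.3 does specify between-arm tests, and permission to do more later is not prespecification.

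Three stronger readings are tempting, and the documents do not support them.
- A reader might infer that ignoring baseline biases the comparison. It does not: the score precedes assignment, and pre-existing symptoms are balanced in expectation.
- A reader might infer a large gain. At r = 0.7 the same simulation gives 14 to 15 points of power, but nothing in the documents supports so high a correlation between one pre-treatment score and a maximum over about 12 booklets.
- A reader might infer that the maximum should be confined to a fixed run of Day 1 booklets common to both arms. That would discard the end-of-treatment booklet, leave patients who stop after one on-study cycle with no outcome, and depart from the plan's use of all available scores. Those patients may have tolerated treatment worst.

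**Conclusion.** The point holds as a cheap improvement, not as an error. The planned chi-square or Fisher comparison is valid and unbiased but less efficient than it could be. Under assumed correlations of 0.3 to 0.5, adjusting for the pre-registration item score lowers the variance of the arm difference by about 1 to 14%, or roughly 0 to 6 points of power. The upper end needs common severe scores and common baseline symptoms. The lower end applies to items with rare severe scores or few baseline symptoms; numbness may be one of the latter, since 3.2.8 excludes grade 2 or higher neuropathy. The correlation, the cut at 3, the event rates and the effect size are all assumptions. The phrase on baseline characteristics in the imputation model may or may not cover the item score, but either way it does not adjust the comparison. DFS and OS are unaffected.

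**What to change.** In 13.4.3, for the first 12 cycles only:

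1. Keep the raw table of maxima and the chi-square or Fisher test.
2. Beside them, prespecify a baseline-adjusted comparison of each item's maximum (3 or higher, or yes/no for rash): logistic regression on arm and the pre-registration item score, reported as a standardised (marginal) risk difference with its confidence interval.
3. Keep patients without a baseline booklet by means of a missing-score indicator.
4. For sparse items, use Fisher's exact test only, with the sparseness threshold stated in advance.
5. Name the baseline item score in the multiple imputation model.
6. State that the maximum uses all available booklets completed after the first on-study dose, including the end-of-treatment booklet for patients who stop early.

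The cost is SAP wording and one extra model per item, with no new data. Two downsides remain: a missing-baseline rule is needed, and for patients given Cycle 1 of mFOLFOX6 before registration the baseline may already contain some toxicity. It is still measured before randomisation, so it remains a legitimate covariate.

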### 13.5 Adverse Event Stopping Rule

The monitoring rules specified below are based on the knowledge available at study development. We note that the Adverse Event Stopping Rule may be adjusted in the event of either (1) the study re-opening to accrual, or (2) at any time during the conduct of the trial and in consideration of newly acquired information regarding the adverse event profile of the treatment(s) under investigation. The study team may choose to suspend accrual because of unexpected adverse event profiles that have not crossed the specified rule below.

Death within 60 days is a tool that has proved useful in reviewing adverse event data as it removes any possible subjectivity. It has the caveat of including all deaths, from any cause, even those not related to therapy [41]. The following table provides a listing of the death rate seen in other large randomized trials in stage III or II/III colon cancer [8, 42-45]. Note: a consistent metric has not been used for all of these trials. Some studies have utilized a 'pure' 60-day all-cause mortality rate, whereas others have excluded deaths not felt to be due to treatment.

Trial	Experimental Arm		Control Arm	
	Regimen	Death Rate	Regimen	Death Rate
X-ACT	Capecitabine	0.80%	5FU/LV	1.03%
MOSAIC	FOLFOX	0.54%	LV5FU2	0.54%
NSABP C-07	FLOX	1.25%	5FU/LV	1.16%
NSABP C-08 (death within 60 days)	FOLFOX+bevacizumab	0.96%	FOLFOX	0.90%
N0147	FOLFOX+cetuximab	0.70%	FOLFOX	0.10%

(death within 60 days)				
------------------------	--	--	--	--

Based on these experiences, we consider a rate of death within 60 days of 1.25% on the mFOLFOX6+atezo arm as the upper threshold of acceptability for this trial. We will monitor this rate continuously. If at any time the 80% two-sided confidence interval for the rate of death within the first 60 days after initiation of mFOLFOX6+atezo excludes 1.25% to the right (i.e. only includes values greater than 1.25%), the Alliance Data Safety Monitoring Board (DSMB) and CTEP will be immediately notified to discuss the possible need to enact a protocol amendment or to discontinue the trial.

This study will be monitored by the Alliance DSMB, an NCI-approved functioning body. Reports containing efficacy, adverse event, and administrative information will be provided to the DSMB every six months as per NCI guidelines.

### 13.6 Protocol-specific Monitoring Plan

This trial will utilize both central and on-site monitoring in order to ensure complete and consistent data collection.

#### Central Data Monitoring and Source Data Verification

Centralized data monitoring activities will be performed for the first three treatment cycles for the first two patient cases enrolled at each site (as identified by a unique CTEP Institution Code) and then for every fourth patient case enrolled thereafter at the site. The cases selected for central data monitoring will be reviewed for completeness and consistency via source data verification (SDV) with source documents compared to the data reported via the electronic Case Report Forms in Rave. Central data monitoring with SDV will be performed for all patients for key eligibility and response/disease outcomes.

A source document is a document in which data collected for a clinical trial is first recorded. This data is usually later entered in the Case Report Forms. The ICH-GCP guidelines define source documents as original documents, data, and records.

The following data and documents will be reviewed via centralized data monitoring and source documents should be uploaded within the two weeks after registration:

- 1) **Informed Consent:** Deidentified last page of the signed and dated informed consent document including any pages with responses indicated by patient for optional studies (patient's full signature should be redacted, but date should be retained).
- 2) **Key Eligibility Criteria:**
  - a. Documentation of Disease: MMR laboratory report.
  - b. Disease Status: Pathology report, operative report, imaging reports, and additional relevant source documents.
  - c. Prior Treatment: Clinic notes and other relevant source documents.
  - d. Comorbid Conditions: Pathology report, laboratory reports, clinic notes, and other relevant source documents.

See the Data Submission Schedule, available on the Alliance and CTSU websites, for additional details regarding source data verification of key eligibility criteria.

- 3) **Treatment Verification/IP Administration:** Applicable drug administration and dosing records to document the first three cycles of treatment.
- 4) **Laboratory Test Results:** laboratory reports, clinic notes (if applicable)
- 5) **Disease Evaluations:** Applicable radiology, imaging assessment, and colonoscopy reports to document disease evaluations and primary endpoint.

Sites should ensure that patient identifiers have been removed from all pages that will be uploaded and add study-specific identifying information (i.e. Alliance Patient ID) and then scan and upload all documents to Rave. Please ensure that all pages are legible and correct.

In the event central monitoring or review of performance indicators (KPIs) identify deficiencies, then additional central monitoring, an unscheduled on-site monitoring visit, or an audit visit may be triggered. Deficiencies or KPIs that may elicit one of these responses include, but are not limited to:

- Accrual rate
- Eligibility
- Early termination
- Data submission timeliness
- Outstanding forms
- Outstanding queries
- Query responsiveness
- Protocol deviations

